#### 1.9.2 The frequency of analyses:

There will be no interim analysis; all data will be analyzed upon completion of all follow-up assessments.

#### 1.9.3 Planned subgroup analyses:

Subgroup analysis of primary and secondary outcomes will be according to risk condition (being born to a diabetic mother or SGA) and sex. The p-value for these analyses will be adjusted to account for multiple comparisons (Bonferroni adjustment).

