#### 1.6.1 Inclusion criteria:

Infants admitted to the well-baby unit at Sinai Health whose parent(s) intend to feed parent milk and who require supplementation:

- Infants of gestational/ type 1/ type 2 diabetic mothers
- Infants who are born small for gestational age (SGA) by using a sex-specific reference population and determining if their birth weight falls below the 10th percentile for gestational age
- Infants with a birth weight less than 2.5 kg

Note: Families will be approached according to the above stated criteria however only registered for trial participation if consent is secured and the infant require supplementation.

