#### 1.6.4 Practical arrangements for allocating participants to trial groups

Families will be invited to participate in the trial during their antenatal visits to the diabetes and placenta clinics. If they agree to participate, they will be asked to sign the consent form. After giving birth, upon admission to the well-baby unit they will be approached again for confirmation of their willingness to participate in the trial and to add infant's name to the consent form. Infants who are prescribed a supplement will be entered into the trial and randomly assigned to either the donor milk or formula group. Prior to the start of the study, a unique randomization schedule will be generated. The computer-generated randomization schedule will be securely stored in a sealed binder, with each participant's allocation placed in separate envelopes. These envelopes will be securely held in a locked procedure room, either within the well-baby unit. Importantly, to maintain blinding, the study coordinator will access the randomization schedule one envelope at a time during participant enrollment and allocation. This approach ensures that the study coordinator cannot see whether a participant will receive donor milk or formula until the point of assignment. The study allocation will be randomly assigned in a 1:1 ratio, using random blocks of 2 or 4. Furthermore, to prevent potential bias and uphold the integrity of the randomization process, the randomization schedule will incorporate stratification factors. These factors include whether the infant was born to a diabetic mother, whether they are small for gestational age, and the infant's sex. Stratification will facilitate the equitable distribution of supplementation rates across these distinct groups, thereby contributing to the robustness of the randomization process.

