#### 1.8 Sample size estimation and power calculations

According to the systematic scoping review of McCune and Perrin published in January 2021, there are no data from RCTs comparing donor milk to formula for supplementation of late preterm or term newborns (13). The only available RCT is a pilot study that assessed the feasibility of using donor milk versus formula for a small group of 32 full-term and late preterm infants admitted to NICU; even though this study did assess certain aspects related to breastfeeding, such as feeding attempts and growth, the authors emphasized the need for larger-scale studies to validate the findings of this pilot study (15). The current exclusive breastfeeding rate in Toronto at 4 months of age is 28% (31). In one retrospective review following donor milk supplementation in late preterm and term newborns ( $\geq$ 35 weeks gestational age), the rate of exclusive breastfeeding rate to 56% would be clinically significant and plausible given the published data and was thus used for sample size calculation. With 80% power and an alpha level of 0.05, we require 47 infants in each of the two study arms. We anticipate, based on our prior work, a 15% loss to follow-up to 4 months of age (32); hence 56 infants will be recruited for each study arm or 112 infants in total.

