#### 1.9 Analyses

#### 1.9.1 The proposed type of analyses:

Analyses will be carried out using SAS Version 9.4. Descriptive statistics will be calculated for all variables of interest. Unadjusted and adjusted models will be run to compare primary, secondary and exploratory outcomes. The primary outcome of exclusive human milk feeding will be compared between groups using a linear regression model. Secondary and exploratory outcomes will be assessed using linear and logistic regression models based on the nature of the outcome measure. The models will be adjusted for risk condition (being born to a diabetic mother or SGA) and sex. The primary analysis for this intent-to-treat study will include all infants as randomized, regardless of feeding protocol compliance.

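### Section 1.9.3 fixes a Bonferroni rule for subgroups without saying which p-value or how many tests, names no interaction test, and uses a risk condition that does not match the randomisation factors

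*Protocol*

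**What the plan says.** Protocol section 1.9.3 consists of two sentences. The first sets the factors and the outcomes: "Subgroup analysis of primary and secondary outcomes will be according to risk condition (being born to a diabetic mother or SGA) and sex". The second sets the inference: "The p-value for these analyses will be adjusted to account for multiple comparisons (Bonferroni adjustment"). No section mentions a treatment-by-subgroup interaction, and none excludes one. The number of comparisons is not given.

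Three other sections bear on the risk condition:

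- **Section 1.6.1 (eligibility)** lists three groups: "Infants of gestational/ type 1/ type 2 diabetic mothers", infants small for gestational age (SGA), and "Infants with a birth weight less than 2.5 kg".
- **Section 1.6.4 (randomisation)** treats diabetic mother and SGA as separate stratification factors: "These factors include whether the infant was born to a diabetic mother, whether they are small for gestational age, and the infant's sex".
- **Section 1.9.1 (models)** uses the merged form again: "The models will be adjusted for risk condition (being born to a diabetic mother or SGA) and sex".

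**The concern.** A p-value within a subgroup answers whether there is an effect in that subgroup. It does not answer whether the effect differs from that in the other subgroup, which is the usual purpose of a subgroup analysis. Bonferroni makes each within-subgroup test stricter but does not change the question it answers. In a trial sized for one overall comparison, each half has low power. Under a uniform effect, one half will therefore often be significant and the other not, and the trial report could present this as donor milk working in one sex or risk group only.

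The risk condition adds a separate problem of definition. An infant can be both SGA and born to a diabetic mother. An infant admitted only because of low birth weight is neither. Section 1.9.3 gives no rule for either case.

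**Working it through.** **Inputs.** From section 1.8: 28% exclusive feeding under formula, 56% under donor milk, alpha 0.05, 80% power, 47 evaluable infants per arm, and 15% loss giving 56 recruited per arm. Two-sided testing is assumed because the protocol does not state it. Subgroup sizes and the number of comparisons are not in the protocol. I assume equal halves, 47 / 2 = 23.5 per arm, and vary the number of tests.

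**The plan's own figure.** Pooled two-proportion formula, mean rate 0.42:

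n = [1.960 × √(2 × 0.42 × 0.58) + 0.842 × √(0.28 × 0.72 + 0.56 × 0.44)]² / 0.28² = 47.6, so 48 per arm.

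This agrees with the stated 47 to within one infant, and power at 47 is 79.5%. For loss to follow-up, 47 / 0.85 = 55.3, so 56 as stated.

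**Power within one half, same true effect in both.** Standard error under the null: √(2 × 0.42 × 0.58 / 23.5) = 0.1440. Under the alternative: √((0.28 × 0.72 + 0.56 × 0.44) / 23.5) = 0.1381. Power p = Φ((0.28 − z × 0.1440) / 0.1381), where z is the two-sided critical value at 0.05 / k for k tests. The two halves are independent, so the chance that exactly one is significant is 2p(1 − p).

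| Tests k | Alpha per test | z | Power per half | Exactly one significant |
|---|---|---|---|---|
| 1 | 0.05 | 1.960 | 49% | 50% |
| 2 | 0.025 | 2.241 | 38% | 47% |
| 4 | 0.0125 | 2.498 | 28% | 40% |
| 8 | 0.00625 | 2.734 | 21% | 33% |
| 20 | 0.0025 | 3.023 | 13% | 23% |
| 40 | 0.00125 | 3.227 | 9% | 16% |

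The figure falls as k grows only because both halves then tend to miss. With unequal splits of 60:40 and 70:30 it is 48% and 51% at two tests, and 41% and 44% at four.

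**Interaction test, same scenario.** A simulation of 200,000 trials with 23 per arm per half, testing the difference between the two risk differences, signals a difference in 6.1% at alpha 0.05, 3.2% at 0.025 and 1.7% at 0.0125. The slight excess over nominal is a small-sample effect.

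**No true effect anywhere.** The chance of any significant subgroup is 1 − 0.975² = 4.9% with two tests and 1 − 0.9875⁴ = 4.9% with four. Unadjusted, it is 9.8% and 18.5%. Here Bonferroni does what it is meant to do.

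**Power of the interaction test.** Standard error of the difference in effects: √2 × 0.1381 = 0.1953. For a 28-point difference in effect between halves, 0.28 / 0.1953 = 1.434. Power at unadjusted 0.05 is Φ(1.434 − 1.960) = 30%. With Bonferroni over three interactions (alpha 0.0167, z = 2.394) it is Φ(1.434 − 2.394) = 17%.

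**The risk condition.** The three groups of section 1.6.1 compare with the later sections as follows:

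| Eligibility group | Randomisation (1.6.4) | Covariate (1.9.1) and subgroup (1.9.3) |
|---|---|---|
| Diabetic mother | own factor | merged |
| SGA | own factor | merged |
| Under 2.5 kg | not named | not named |

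The low-weight group need not be small. Table 1 in section 1.10 implies 318 × 0.88 ≈ 280 supplemented infants under 2.5 kg a year, against 501 × 0.74 ≈ 371 with diabetic mothers. How many of the 280 are neither SGA nor born to a diabetic mother is not given.

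**The case against.** The strongest reply is that the protocol is silent rather than wrong. The second sentence of section 1.9.3 fits an interaction p-value as well as a within-subgroup one, and the form of a subgroup test is often left to a statistical analysis plan, which is not at hand here. That stands to this extent: a reader might infer that the protocol has rejected interaction tests, and the text does not support that. But section 1.9.3 does not defer the question. It fixes an inferential rule, and the rule cannot be applied as written without knowing which p-values it covers and how many.

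A reader might also infer that false subgroup differences are likely. That holds only if there is a real overall effect and if someone compares significance across subgroups, which no section plans to do. With no effect, Bonferroni holds. The size also depends on the number of tests: section 1.9.3 covers secondary outcomes too, so the divisor could be well above four, and the figure then falls towards 16%.

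A third inference, that overlap and the unnamed weight group raise the false-difference rate, does not follow. They affect who is counted where. Nor does the text show that weight-only infants leave the primary analysis, since section 1.9.1 includes all infants as randomised. If the risk condition means either versus neither, or the two separate randomisation factors, every infant already has a place. The protocol does not say which of these is meant.

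Lastly, interaction tests here are weak and need their own multiplicity rule: three at 0.05 would give 1 − 0.95³ = 14% false signals if independent. This is a fair point, and the fix takes it up.

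**Conclusion.** The point holds in a limited form. Section 1.9.3 states one rule for subgroup inference, does not identify the p-value or the number of comparisons, and mentions no test of whether effects differ. On the natural within-subgroup reading, a uniform 28% vs 56% effect gives exactly one significant half in 40% to 47% of trials with four or two tests, and 16% to 33% with forty to eight, against about 6% for an interaction test at 0.05 (about 2% to 3% at the alpha for four or two tests). These figures rest on equal halves of the 47 evaluable infants per arm, two-sided testing, one pair of subgroups and the primary outcome.

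The mismatch between the merged risk condition and the separate randomisation factors is a second, documentary inconsistency. Its cost lies in coverage and interpretation. The overall treatment comparison is not called into question by either part.

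**What to change.** Reword section 1.9.3 as follows:

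1. Assess subgroup differences by a treatment-by-factor interaction for each randomisation factor: diabetic mother yes/no, SGA yes/no, and sex. State the effect scale.
2. Apply the Bonferroni adjustment to these interaction p-values and state the number of tests, including how secondary outcomes count.
3. Report the treatment effect with a 95% CI in each level, and label any claim of a differential effect exploratory.
4. Code the risk condition in section 1.9.1 as the same two separate yes/no factors.

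Infants with both conditions are then yes on both factors, and infants eligible only by weight are no on both and stay in the analysis.

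The cost is a few sentences and a few extra model terms, with no new data. The drawback is low power: about 30% for a 28-point difference in effect between halves at unadjusted 0.05, and about 17% after adjustment for three tests. A non-significant interaction should therefore not be reported as evidence of a uniform effect.

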#### 1.9.4 Any pilot study been carried out using this design:

The systematic scoping review of McCune et al. (13) reported on 5 observational studies (donor milk n= 696 and control n=385) and a single RCT (donor milk n=30 and control n=30). The observational studies showed improvements in breastfeeding outcomes while the RCT did not, however, the control arm was exclusive breastfeeding not formula supplementation. A very recent pilot RCT that investigated the use of donor milk versus formula in 32 term and late preterm infants admitted to NICU confirmed the feasibility of randomly assigning term and late preterm infants into donor milk or formula groups when their mother's milk is not available, and showed that donor milk may increase breastfeeding attempts without having a negative effect on growth (15).

### **1.10 Rationale for recruitment target**

There are more than 6000 admissions to the well-baby unit at Sinai Health annually with approximately 15% being "at higher risk for supplementation" and typical supplementation rates of about 80%. This makes our timeline of recruiting 112 infants in 12 months (approximately 2-3 infants per week) very realistic (Table 1).

Table 1: Annual admissions to Sinai Health's well-baby unit according to risk group for supplementation

Year: 2020	Number	Supplemented
Total	6326	52%
Diabetic mother	501	74%
< 2.5 kg	318	88%

# 1.11 Project milestones and timeline

[figure not shown]
The planned trial will take 6 months of start-up time and 12 months of recruitment (Table 2 and Figure 1). Final patient follow-up assessments, data analysis and end of grant knowledge translation are planned for the final 5 months. The full project will be completed by March 31, 2025.

#### Table 2: Study Timeline

Task	2023 Apr-Jun	2023 Jul-Sep	2023 Oct- Dec	2024 Jan- Mar	2024 Apr-Jun	2024 Jul-Sep	2024 Oct- Dec	2025 Jan- Mar
Trial preparation Protocol development Trial logistics development REB submission Training on outcome tools Staff in-servicing								
Trial management Patient recruitment Trial intervention Patients follow up Data collection								
Post trial completion Data analysis Manuscript preparation Knowledge translation								

Figure 1: Summary of study follow up and timing

In the case of multiple gestations (twins), each twin will be assigned to a different group, using a separate randomization plan with blocks of two, allowing for more precise comparisons and analysis. When two parents are available, both parents will be asked to separately complete the questionnaires.

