#### 1.6.5. Communication of group allocation with the nursing staff and parent(s):

The responsibility for communicating group allocation lies with the study coordinator. Following the completion of the randomization process, parents and nursing staff will be informed of the group allocation, as the study is open-label, and this information aligns with the study design. During this discussion, parents will receive a clear explanation of their infants' group assignment, including its implications and details regarding the associated supplementation. It will also emphasize the voluntary nature of participation and the option for parents to withdraw from the study at any point.

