#### Exclusive human milk feeding and informal shared milk feeding:

As previously mentioned, parent report will be taken at 1, 2, 3, and 4 months. At each interaction, participants will be asked whether the infant is receiving any human milk (yes/ no) and about exclusive human milk feeding. Exclusive human milk feeding will be defined as the provision of only human milk with no additional fluids (including water) or solids except for vitamins/minerals and medicine (including rehydration solutions). Based on previous research, we will explore human milk feeding "at" each time-point (within the previous 2 weeks of the interaction) as well as "for" each time interval (e.g., from hospital discharge to 4 months) (20). We anticipate the intervention will increase both the duration and exclusivity of human milk feeding due to the value given to human milk provision in this study. In order to understand the potential impact of increased informal milk sharing in situations where donor milk is not available after hospital discharge, we will investigate the frequency of this practice. To gather this information, we will include questions in our monthly check-in questionnaire for parents. Specifically, we will ask parents to indicate the number of times per day their infant was fed expressed human milk using a bottle, supplemental nurser, or other methods. Additionally, we will inquire whether the milk used for these feedings was expressed by the parent themselves or by someone else or whether it was a non-human milk based formula. By collecting this data, we aim to gain insights into the prevalence of informal milk sharing and its potential implications for infant feeding practices.

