#### Breastfeeding self-efficacy (Breastfeeding Self-Efficacy Scale):

This will be administered at each time-point post hospital discharge to assess the trajectory of feeding practices. A parent's perception of their ability to breastfeed has been shown to predict both duration and exclusivity of breastfeeding (23). A tool to measure this perception has been developed by Dennis et al. and validated in Canada. This has been updated to a shortened version (Breastfeeding Self-Efficacy Scale – Short Form, BSES-SF) which consists of 14 items scored on a 5-point Likert scale ranging from not at all confident to always confident (24). Understanding parent's feeding self-efficacy provides important context to the duration and exclusivity of human milk feeding as well as infant growth throughout early infancy; it is possible that low breastfeeding self-efficacy may confound exclusive human milk feeding at 4 months of age. Further these outcomes may illustrate areas for intervention to support the duration and exclusivity of human milk feeding and growth among infants admitted to a well-baby unit following birth.

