#### Parental stress, anxiety and depression:

Very little is known about the relationship between donor milk and parental mental health; this has been highlighted as an area requiring further study (25). Two well-established self-reported assessment tools will be employed to measure parental mental health at 2 and 4 months CA. For families with two parents, both will be asked to independently complete the same questionnaires. Anxiety will be measured with State-Trait Anxiety Inventory (STAI) which has been used to assess trait (20 items) and state (20 items) anxiety. This tool has been validated in different populations including postpartum women (26). STAI has been used to differentiate anxiety from depressive syndromes and to generally assess caregiver distress in research (27). The Edinburgh Postnatal Depression Scale (EPDS) has been classically described for screening for postpartum depression in mothers using a 10-point scale. There is evidence for its validity in fathers and therefore all parents will be invited to complete this screening. The measurement of these outcomes will also allow us to explore how they may impact the duration and exclusivity of human milk feeding at 4 months.

If a participant fills out the survey through our online survey platform, REDCap, and their response to the EPDS suggests a high likelihood of depression or self-harm, we have a well-defined protocol in place to prioritize their safety. Within 24 hours of receiving such a response, our study team will be immediately notified. We will then promptly contact the participant, providing them with clear and detailed instructions on how to access the necessary help and support. This may involve connecting them with a healthcare professional or emergency services as needed. If the survey is conducted via a phone conversation or in-person interaction, we will provide specialized guidance right away in the event of similar concerns.

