#### Milk cortisol:

Milk cortisol is known to be associated with maternal distress and may play an important role in programming infant response to parental stress and may be related to infant growth (28, 29). Timed milk samples (morning sample to account for diurnal variation) will be collected at 2 and 4 months of age. These samples will be collected in the morning, within two hours after waking up, to account for the natural rise in cortisol levels during this time. We aim to collect these samples preferably between 6:30 AM and 8:30 AM. This timing consistency aligns with the screening tool for parental stress, anxiety, and depression questionnaires, which will also be administered at similar time points. Cortisol concentrations will be guantified using an enzymelinked immunosorbent (ELISA) assay or liquid chromatography-tandem mass spectrometry (LC-MS/MS) in [name] [name]'s laboratory at the University of Toronto In order to facilitate the milk sample collection process for our participants, we will ensure that special containers designed for this purpose are readily available to them. Our commitment to participant convenience and clarity extends to providing comprehensive instructions. These instructions will not only outline the precise methods and timing for collecting milk samples but will also specify the appropriate storage conditions, with an emphasis on keeping the samples stored in a -20°C freezer. Additionally, participants will receive guidance on the logistics of sending these samples to [name] [name]'s laboratory via courier. Furthermore, for those who opt for an inperson 4-month visit, the option to bring the samples with them will be made available, ensuring flexibility and ease in the participation process.

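### Twins are split between arms to gain precision, but the analysis models ignore the pair, and split-twin families have no arm for parent-level outcomes

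*Protocol*

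**What the plan says.** The text under Figure 1 in section 1.11 puts the two members of a twin pair in opposite arms. They are "assigned to a different group, using a separate randomization plan with blocks of two, allowing for more precise comparisons and analysis". Precision is the only reason given.

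Section 1.9.1 compares the primary outcome, exclusive human milk feeding at 4 months, by linear regression, and the other outcomes by linear or logistic regression. Unadjusted and adjusted versions are planned: "The models will be adjusted for risk condition (being born to a diabetic mother or SGA) and sex". On the analysis set it says: "The primary analysis for this intent-to-treat study will include all infants as randomized, regardless of feeding protocol compliance". Both twins therefore enter. No pair or family term, random effect, clustered variance or other rule for multiples appears in the protocol, and the sample size section (1.8) does not mention twins.

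Several outcomes in section 1.7 are measured on the parent:

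- The BSES-SF (secondary) measures the parent's own confidence: "A parent's perception of their ability to breastfeed has been shown to predict both duration and exclusivity of breastfeeding".
- For the STAI and EPDS (exploratory): "For families with two parents, both will be asked to independently complete the same questionnaires".
- For milk cortisol (exploratory): "Timed milk samples (morning sample to account for diurnal variation) will be collected at 2 and 4 months of age".

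**The concern.** The twin pair is a unit by which the trial randomizes, yet the models leave it out. If twins' outcomes are positively correlated, splitting pairs makes the arm difference less variable than the same number of unrelated infants would. A standard error that assumes independence misses this, so the gain that justifies the split does not reach the confidence interval or the p-value.

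The parent-level problem is different. A parent with one twin in each arm has been exposed to both allocations and has one score, so that family carries no arm contrast. No pair term can restore it. If the one score were entered in both arms, the estimated difference would shrink toward zero. The protocol does not plan this, but it does not rule it out either.

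**Working it through.** **The plan's own figure.** Inputs from section 1.8: 28% versus 56%, alpha 0.05 (two-sided assumed), 80% power, 15% loss. The pooled-variance formula without continuity correction gives 48 per arm (stated 47; power at 47 is 79.5%), and 47/0.85 = 55.3, rounded up to 56. The stated sample size reproduces and is not in question. The calculations below use 96 evaluable infants (2 × 48; 112 × 0.85 = 95.2).

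**Assumptions.** The protocol gives neither the number of twin pairs nor their correlation. The ranges used are 2, 5 or 10 pairs (s = 4/96, 10/96, 20/96, or 4%, 10%, 21% of infants) and an observed within-pair correlation r of 0.33, 0.59 or 0.84.

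**Closed form under no effect.** With n per arm, m split pairs and outcome variance σ²:

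Var(difference) = 2σ²/n − 2m·rσ²/n² = (2σ²/n)(1 − r·s), where s = m/n.

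The independence standard error uses 2σ²/n, so it is too large by the factor 1/√(1 − r·s). Example: r = 0.84 and 5 pairs give r·s = 0.0875 and 1/√0.9125 = 1.047. The type I error of the unpaired test is 2·(1 − Φ(1.96/√(1 − r·s))), here 4.0%. At a common rate of 42% the independence standard error is √(2 × 0.42 × 0.58/48) = 0.1007. The simulated true values for r = 0.84 are 0.0989, 0.0967 and 0.0912 for 2, 5 and 10 pairs.

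Each cell shows the excess in the standard error, then the simulated type I error with the pair ignored (40,000 runs per cell, linear model, no covariates):

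| r | 2 pairs | 5 pairs | 10 pairs |
|---|---|---|---|
| 0.84 | 1.8%; 4.6% | 4.7%; 4.0% | 10.1%; 3.0% |
| 0.59 | 1.3%; 4.7% | 3.2%; 4.4% | 6.8%; 3.6% |
| 0.33 | 0.7%; 4.8% | 1.8%; 4.6% | 3.6%; 4.2% |

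Cluster-robust standard errors bring the type I error to 4.7% to 5.2% in all nine cells.

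**Power for 28% versus 56%.** One parent feeds both twins and knows both allocations, so the effect within a split pair may be anything from zero to full. Power with independence, then cluster-robust, standard errors at r = 0.84:

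| Within-pair effect | 2 pairs | 5 pairs | 10 pairs |
|---|---|---|---|
| Zero | 77.3% → 77.6% | 72.3% → 74.9% | 61.2% → 68.8% |
| Half | 79.1% → 79.4% | 77.0% → 78.8% | 72.6% → 78.9% |
| Full | 80.8% → 81.0% | 81.3% → 82.2% | 81.5% → 85.1% |

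The power forgone is 0.2 to 0.3 points with 2 pairs, 0.9 to 2.6 with 5 and 3.6 to 7.6 with 10. With 10 pairs it is about 3 to 5 points at r = 0.59 and about 2 at r = 0.33. An analytic check with 47 per arm and a full within-pair effect agrees in direction and size: 80.1% versus 81.6% at a 10% twin share and correlation 0.5, and 81.6% versus 86.1% at 20% and 0.8.

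**Parent-level outcomes.** If one parental value is entered in both arms, split pairs contribute a difference of exactly zero and the expected difference is multiplied by 1 − s: 0.96, 0.90 and 0.79. For an assumed true difference of 0.58 SD (about 80% power at 48 per arm), power is then 77%, 71% and 62%. With those families left out it is 78%, 75% and 70%.

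**The case against.** The strongest reply is that section 1.9.1 names model type, covariates and population but no variance estimator. A linear regression with cluster-robust standard errors, adjusted for risk condition and sex on all randomized infants, fits the text as it stands, and handling of multiples could be left to a statistical analysis plan. The precision statement is also true of the design: splitting pairs does lower the variance. This carries weight, and it is one reason the point is minor. It does not remove it. The protocol claims the gain and names its models and full adjustment set without the pair, and the ordinary reading of those models is one of independent infants.

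It is also fair that the size rests on two unstated quantities and that the top of the range needs 21% twins, r = 0.84 and no within-pair effect together. Adjustment for maternal diabetes, which twins share, would absorb part of the correlation. The parent-level shrinkage is conditional on a data-entry choice that nobody has announced. All of this stands. What remains is that the protocol gives no arm to split-twin parents.

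Finally, dilution of the effect within pairs can cost more than the standard error does: at 10 pairs and r = 0.84, unpaired power falls from 81.5% (full effect) to 61.2% (none), and clustering recovers 7.6 points. That is correct, and the fix below does not claim to cure it. Placing both twins in the same arm is a separate trade-off.

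**Conclusion.** The concern holds as a minor point. Followed literally, the models ignore a unit of randomization and report a standard error that is too large whenever twins' outcomes are positively correlated. The error is conservative: it creates no false positives and leaves the stated sample size intact. It is negligible with 2 pairs, becomes visible at about 5, and at 10 pairs with high correlation costs up to about 8 points of power. These sizes depend on the assumed twin share and correlation. For the BSES-SF, STAI, EPDS and milk cortisol, split-twin families have no arm contrast by design; attenuation follows only if one value is counted in both arms.

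**What to change.** Add to section 1.9.1:

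> In all infant-level models the family is the cluster, with cluster-robust standard errors and an independence working correlation; a singleton is a cluster of one. Families whose twins are in opposite arms are left out of between-arm comparisons of parent-level outcomes (BSES-SF, STAI, EPDS, milk cortisol). The primary result is also reported without twins as a sensitivity analysis.

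Exchangeable-correlation GEE should not be the stated method. It gives split pairs more weight, and these are where the effect may be diluted: "parents and nursing staff will be informed of the group allocation, as the study is open-label", and the expected benefit is put down to a parental mechanism, "due to the value given to human milk provision in this study". At r = 0.84 with no within-pair effect, exchangeable GEE cuts the mean difference from 25.1 to 14.5 points and power from 72.3% (unpaired analysis) to 61.8% with 5 pairs, and from 22.2 to 10.0 points and 61.2% to 46.6% with 10. It gains only when pairs are many and the within-pair effect is nearly full (86.5% against 85.1% for cluster-robust at 10 pairs).

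The cost is three sentences, one extra analysis and a few parent-level observations (5 families at a 10% twin share). The linear model with cluster-robust standard errors lost no power in any of the 27 non-null scenarios, and a logistic model lost none beyond rounding. The analysis without twins has lower power, about 78%, 76% and 70% for 2, 5 and 10 pairs, so it should stay secondary.
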